11.3.3 Analysis of additional measures

The same analysis strategies will be applied to the additional measures. For continuous measures, the difference between the two treatment groups will be assessed by t-test statistics. The impact of the two stratification variables on the outcomes between the two groups will also be explored, and reported if the test suggests a difference. If the parametric assumptions are not met, nonparametric methods will be used. Survival analysis techniques such as Kaplan-Meier or Cox Proportional Hazards will be incorporated if censoring of data occurs.

Key components of the additional measures may also be compared, including specific adverse events associated with the procedure, such as vessel rupture or tear.

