7.5.3 Additional Measures

- Anatomic success
- Clinical success
- Adverse events (refer to Section 9.6: Adverse Events for a list of reportable events)
- Primary patency through 90 days

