11.3 Analyses

11.3.1 Primary endpoint analysis

The study is intended to compare the necessity of adjunctive therapies for lesions treated with the study device (Enforcer balloon) compared to those treated with the control device (conventional angioplasty balloon inflated to standard pressures). The null (H_0) and alternative (H_A) hypotheses are expressed as follows:

$H_0: AT_{EB} \geq AT_{CA}$

$H_A: AT_{EB} < AT_{CA}$

where AT_{EB} is the rate of adjunctive therapies in the Enforcer balloon group and AT_{CA} is the rate of adjunctive therapies in the conventional angioplasty balloon group.

The rates of adjunctive therapies will be compared between the two treatment groups with a one-sided Z-test. A p-value $< .05$ will be used to claim statistical significance. If the number of patients within each strata are sufficiently large, the association of stratification factors and treatment will be assessed. Crude and adjusted, if applied, differences in rate of adjunctive therapies between the two treatment groups and 95% confidence intervals will be reported.

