11.3.2 Analysis of secondary endpoints

Differences in pain, procedural costs, procedure times, and maximum balloon pressure will be assessed overall by one-sided t-tests, with Enforcer balloon having favorable outcomes. In addition, regression models will be used to incorporate the stratification factors as covariates and reported if found to be significant. If the parametric assumptions are not met, nonparametric methods will be used. The safety claim will be evaluated with a Z-statistic, with a non-inferiority of Enforcer balloon at a margin of 10%. The observed non-inferiority margin will also be presented.

Adjustments for multiplicity will be made using the Holm procedure to control the family-wise error rate to 0.05 across the family of secondary endpoints.

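### Section 11.3.3 hands adverse events over to a one-sided test for fewer events on Enforcer or a 10-point non-inferiority test, neither of which is designed to show an excess of harm

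*Combined protocol and SAP*

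**What the plan says.** Section 7.5.3 lists as an additional measure "Adverse events (refer to Section 9.6: Adverse Events for a list of reportable events"). Section 9.6 makes three groups reportable: events potentially related to device or procedure, serious events, and restenosis or occlusion leading to reintervention or abandonment. They are collected through 90 days.

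For analysis, Section 11.3.3 opens with "The same analysis strategies will be applied to the additional measures". It then names t-tests for continuous measures and Kaplan-Meier or Cox methods if data are censored. It adds that specific procedural events, such as rupture or tear, may be compared, without naming a test. It names no method for comparing the proportion of patients with an event.

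The strategies available to carry over are:

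- Section 11.3.1: "The rates of adjunctive therapies will be compared between the two treatment groups with a one-sided Z-test", with the alternative that the Enforcer rate is lower; p below .05 "will be used to claim statistical significance". The same paragraph promises rate differences with 95% confidence intervals.
- Section 11.3.2, for pain, cost, time and pressure: differences "will be assessed overall by one-sided t-tests, with Enforcer balloon having favorable outcomes".
- Section 11.3.2, for safety: "The safety claim will be evaluated with a Z-statistic, with a non-inferiority of Enforcer balloon at a margin of 10" per cent, followed by "The observed non-inferiority margin will also be presented".
- Section 11.3.2, on multiplicity: "Adjustments for multiplicity will be made using the Holm procedure to control the family-wise error rate to 0.05 across the family of secondary endpoints".

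**The concern.** Adverse events are mostly yes/no outcomes, so the t-test sentence does not help. Of the two proportion tests that could be inherited, one has its whole rejection region on the side of benefit. The other is built to tolerate an excess below 10 points. That margin is widest, relative to the event rate, for the rare procedural events that 11.3.3 itself mentions.

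Two readings are possible. If the carry-over is literal, a nominally significant excess of a rare event can be reported as non-inferior. If it is only a general pointer, the test and direction for adverse events are not fixed before the data are seen. Both readings call for the same few sentences of repair.

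**Working it through.** **The plan's own figure.** The documents give no event rate, sample size or power for adverse events. The only stated calculation is for the primary endpoint: 125 lesions per group, 5% against 15%, 80% power, type I error 0.05 (Section 11.1).

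- One-sided pooled Z: Φ[(0.10 − 1.645·√(2·0.10·0.90/125)) / √((0.05·0.95 + 0.15·0.85)/125)] = Φ[(0.10 − 0.0624)/0.0374] = 84.2%.
- Two-sided, with 1.96 in place of 1.645: 75.3%.
- One-sided Fisher exact: 79.8%.

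The stated 80% fits a one-sided test, so the framework that 11.3.3 inherits is one-sided in its sizing as well as its wording.

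**Inputs and assumptions for adverse events.** About 100 patients per group (Section 11.1), or 125 per group if lesions are the unit. The margin is read as 10 percentage points, because 11.3.2 does not state the scale. The level is one-sided 0.05, unadjusted, with an unpooled standard error and independent observations. Event rates are illustrative.

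**Observed 6/100 on Enforcer, 0/100 on control.**

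- Standard error = √(0.06·0.94/100) = 0.02375.
- Non-inferiority Z = (0.10 − 0.06)/0.02375 = 1.68, above 1.645. The upper bound is 0.06 + 1.645·0.02375 = 9.9 points, so the test passes.
- One-sided pooled Z-test in Enforcer's favour: p = 0.99.
- Two-sided pooled Z-test: p = 0.013. Two-sided Fisher: p = 0.029.
- Newcombe 95% interval: the Wilson limits are 2.78% to 12.48% for 6/100 and 0% to 3.70% for 0/100. Lower limit = 0.06 − √((0.06 − 0.0278)² + 0.0370²) = 0.011. Upper limit = 0.06 + (0.1248 − 0.06) = 0.125.

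**Observed 8/125 against 1/125.** Standard error = √((0.064·0.936 + 0.008·0.992)/125) = 0.0233. The upper bound is 0.056 + 1.645·0.0233 = 9.4 points, which passes. Two-sided Z p = 0.018; Fisher p = 0.036.

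These are boundary cases: 6 is the largest Enforcer count that passes against 0 per 100, and 8 the largest against 1 per 125. At the strictest Holm step with six endpoints assumed (0.05/6), 6 against 0 per 125 still passes, with two-sided Z p = 0.013.

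**Long-run behaviour** (exact binomial enumeration; the two-sided test is pooled Z at 5% in the harm direction):

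| True rates, Enforcer v control | n per group | Declared non-inferior | Two-sided test shows excess | Both |
|---|---|---|---|---|
| 5% v 1% | 100 | 80% | 37% | 19% |
| 5% v 1% | 125 | 82% | 46% | 28% |
| 6% v 1% | 100 | 65% | 49% | 17% |
| 14% v 4% | 100 | 6% | 73% | under 0.1% |
| 12% v 2% | 125 | 7% | 91% | 1% |

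At 14% v 4%, the one-sided test in Enforcer's favour is significant with probability 0.00002.

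**Frequent events.** Section 5.0 gives 62.0% patency at 90 days in the earlier single-arm study. If about 38% have an event in each group, 1.645·√(2·0.38·0.62/n) is 11.3 points at n = 100 and 10.1 points at n = 125. No observed excess could then pass a 10-point margin.

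**The case against.** A reader might infer that an excess of harm cannot be flagged at all, or that the report would carry no inferential signal of it. The documents do not support that, for these reasons:

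- A large excess fails non-inferiority, and the failure is visible, though failing is not a finding of harm.
- Section 11.3.2 requires the observed margin to be presented.
- Section 11.3.3 allows specific events to be compared, and allows survival methods, with no direction stated.
- The Enforcer-favourable direction in 11.3.2 covers four named continuous endpoints and cannot be read onto proportions.
- If the one-sided test of 11.3.1 carries over to adverse events, so on the same logic does its 95% interval for the difference.
- Centralized monitoring (14.0) and event reporting to IRBs and investigators (9.6) do not depend on hypothesis tests.

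All of this stands, and it limits the point to rare events and modest excesses. It does not remove the point. The comparison of specific events is optional and names no method. No sentence says that the interval applies to adverse events. Nothing says which of the two inherited tests governs them.

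It is also fair to object that banning the 10% test for every adverse event would contradict the safety claim, because rupture, circumferential tears and reintervention are both adverse events and secondary safety measures (7.5.2). The fix below keeps them separate.

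**Conclusion.** The point holds in limited form. Section 11.3.3 applies earlier strategies to adverse events, and the only proportion tests among them look for benefit or tolerate an excess. For rare events the second can call a nominally significant excess non-inferior. At true rates of 6% v 1% with 100 per group, non-inferiority is declared 65% of the time, and in 17% of trials alongside a significant two-sided excess. At 14% v 4% it is declared only about 6% of the time, and near 38% event rates no observed excess passes. Harm is therefore not wholly hidden.

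The figures rest on an absolute margin, unadjusted one-sided 0.05, independent observations and illustrative event rates. That adverse events inherit one of these tests is the natural reading of 11.3.3, not an explicit rule. The change is a cheap improvement to the analysis and does not mean that the trial is unsound.

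**What to change.** In Section 11.3.3, take adverse events out of the carry-over sentence and state:

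- Adverse events overall, serious events, device- or procedure-related events and each event type will be reported as the number and percentage of patients with at least one event, by treatment group, with the risk difference (Enforcer minus control) and a two-sided 95% score (Newcombe) confidence interval.
- Neither the one-sided test nor the 10% margin is applied to adverse events as an additional measure.
- For rupture, circumferential tears and reintervention/patency, the safety-claim test of 11.3.2 stays as planned, and the two-sided interval is reported beside it.

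The cost is a few sentences and one table, from data already collected, with no extra patients. The sponsor gives up favourable one-sided or non-inferiority statements on adverse events outside the safety claim. With many event types, some intervals will exclude zero by chance, so the report should present them as descriptive.

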3.0 Objectives of the Clinical Study

The primary objective of this study is to evaluate the necessity of adjunctive therapy following treatment of stenoses of a mature native AV dialysis access circuit fistula or graft with the Enforcer balloon compared to stenoses initially treated with commercially available conventional balloon angioplasty.

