5.0 Background Information

The safety and performance of the Enforcer balloon were assessed through a series of nonclinical tests performed in accordance with verified methods and procedures to maintain the integrity of the results. The testing results provide reasonable assurance that the potential risks associated with the use of the device have been mitigated to an acceptable level. Additionally, conventional balloon angioplasty is a standard treatment for dialysis access dysfunction and several clinical evaluations have been performed and reported in literature, which assess safety and performance of angioplasty using different balloon technologies (e.g., conventional balloons, high pressure balloons, cutting balloons).¹

A prospective, single-arm, single-center clinical evaluation of the Enforcer balloon was previously conducted to evaluate the treatment of AV access stenoses.² The study evaluated the treatment of 39 AV fistula lesions in 28 patients who were treated with 37 Enforcer balloons; patients were followed for 6 months post-procedure. Device success, defined as < 30% residual stenosis immediately following treatment was 64.1% (25/39). Similarly, 92.3% (36/39) of lesions were reduced to < 50% residual stenosis. Overall, treatment with the Enforcer balloon led to a reduction in the average percent diameter stenosis of the treated lesion from 66.3% pre-procedure to 23.7% post-procedure. The average maximum inflation pressure required was 12.3 atm. Only one lesion required adjunctive treatment following angioplasty with the study balloon, indicating that

clinically relevant luminal gains can be achieved with the study device alone, without the need for a high pressure balloon or other additional therapies.

Following the study procedure, all patients could resume normal dialysis. The Kaplan-Meier estimates for patency at 90 days and 6 months were 62.0% and 25.1%, respectively. The rate of access site complications were low (1/28; 3.6%). Overall, the data supported the safety of the Enforcer balloon for the treatment of stenotic lesions in mature native AV hemodialysis access circuits.

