11.0 Statistical Considerations

11.1 Sample Size

The expected rates of adjunctive therapy for the Enforcer balloon and conventional angioplasty groups were assumed to be 5% and 15%, respectively. A sample size of at least 250 total lesions (125 lesions per group) is required to detect a 10% difference in the rate of adjunctive therapy with a power of 80% and a type I error of 0.05. Prior experience suggests that 40% of patients, on average, would also have a second lesion treated. Therefore the study will enroll approximately 200 patients (approximately 100 patients per group) and enrollment will continue until at least 250 lesions are treated. Procedural outcomes are unlikely to depend on the connectivity between lesions within an AV dialysis access circuit or the patient-level factors which affect longer-term outcomes, and therefore lesions were assumed to be independent for the purposes of the sample size calculation.

Up to 10 clinical sites will be included in the study, and the maximum enrollment per clinical site will be no more than 80 patients or 40% of the total enrollment. There is no minimum enrollment threshold. Patients that withdraw from the study will not be replaced.

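### For the additional measures, section 11.3.3 reports the impact of access type and lesion number only if an unspecified test suggests a difference, so what is reported is selected on the test result

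*Combined protocol and SAP*

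**What the plan says.** Section 7.5.3 lists four additional measures: anatomic success, clinical success, adverse events and primary patency through 90 days. Section 11.3.3 governs their analysis. It says that the influence of access type and lesion number "on the outcomes between the two groups will also be explored, and reported if the test suggests a difference". No test, level or multiplicity control is named for this step; the Holm procedure in 11.3.2 covers only the secondary endpoints.

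Other sections use different rules:

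- Primary endpoint (11.3.1): "If the number of patients within each strata are sufficiently large, the association of stratification factors and treatment will be assessed". This condition is on stratum size, with no number given, and not on a p-value. The section adds: "Crude and adjusted, if applied, differences in rate of adjunctive therapies between the two treatment groups and 95% confidence intervals will be reported". Those are overall differences, not differences by stratum.
- Secondary endpoints (11.3.2): "regression models will be used to incorporate the stratification factors as covariates and reported if found to be significant". No treatment-by-factor interaction is named.

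No section commits to showing results by access type or by number of lesions.

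**The concern.** A rule that publishes a subgroup result only when its test is positive has two effects. True differences of moderate size tend to disappear because the test has little power. The differences that do appear include chance findings, and their size is exaggerated.

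This matters here because the objective in section 3.0 covers "stenoses of a mature native AV dialysis access circuit fistula or graft", while the only Enforcer clinical study described in section 5.0 was in fistulas: "The study evaluated the treatment of 39 AV fistula lesions in 28 patients". This trial would therefore supply the first graft data that the plan refers to. The sponsor also judged access type and lesion number important enough to stratify the randomization on both. If nothing is shown by stratum, a reader can only carry the pooled result over to grafts, and cannot tell a stratum that was examined and found similar from one that was too small to show anything.

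**Working it through.** **The plan's own figure.** The plan gives no expected graft share and no power for any stratum comparison. Its one sizing figure is for the overall primary comparison: "A sample size of at least 250 total lesions (125 lesions per group) is required". With 5% against 15%, a one-sided Fisher exact test has 79.8% power at 125 per group, so 250 is reproduced. That sizing makes no provision for comparing effects between strata.

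**Inputs from the documents.** About 100 patients per group, of whom 40% are expected to have a second lesion (11.1). That gives about 60 one-lesion and 40 two-lesion patients per arm. Patency at 90 days in the earlier fistula study was 62.0% (5.0), so loss is about 38%.

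**Assumptions.** The 11.3.3 test is a Wald test of treatment-by-access interaction on the risk-difference scale, two-sided 0.05. Patency loss is treated as binary at 90 days. Graft share is 15% to 40%. Loss is 38% in every cell except Enforcer grafts.

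**Step 1: chance of reporting a graft-only excess of 58% against 38%.** With g grafts and f = 100 − g fistulas per arm:

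SE = √[(0.58×0.42 + 0.38×0.62)/g + 2×0.38×0.62/f]

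Power = Φ(0.20/SE − 1.96) + Φ(−0.20/SE − 1.96)

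| Grafts per arm | SE | Power, formula | Power, simulated | Unreported, simulated |
|---|---|---|---|---|
| 15 | 0.194 | 18% | 21% | 79% |
| 25 | 0.160 | 24% | 26% | 74% |
| 40 | 0.141 | 30% | 31% | 69% |

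The simulation used 400,000 replicates per row. At a 50% graft share power is still only about 31%, so for an effect of this size the conclusion does not depend on the assumed share. The same 20-point excess confined to two-lesion patients (40 per arm) has about 30% power.

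**Step 2: larger effects.** By simulation, with 15, 25 and 40 grafts per arm:

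- A 30-point excess (68% against 38%) is flagged 39%, 50% and 59% of the time.
- A 40-point excess (78% against 38%) is flagged 61%, 75% and 84% of the time.

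**Step 3: size of what gets through.** In the 20-point scenario, the mean absolute interaction among significant results is 46, 40 and 36 points at the three shares, against a true 20.

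**Step 4: chance findings.** Four measures × two factors = 8 tests. If they are independent and each is at 0.05, 1 − 0.95⁸ = 0.337. Without independence, the upper bound is 8 × 0.05 = 0.40.

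**Step 5: precision if every stratum is reported.** Half-width of the 95% CI for the graft difference:

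- Patency loss, 38% in both arms: 1.96√(2×0.38×0.62/g) = 35, 27 and 21 points for g = 15, 25 and 40 patients per arm.
- Adjunctive therapy, 15% in both arms, lesions independent as 11.1 assumes: 1.96√(2×0.15×0.85/n) = 23, 18 and 14 points for n = 19, 31 and 50 lesions per arm (15%, 25% and 40% of 125).

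**The case against.** Several points on the other side are sound and limit the concern.

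- **Scope.** A reader might infer that the primary endpoint is also filtered on significance, so that a failure to reduce adjunctive therapy in grafts would be suppressed. The text does not support that. The 11.3.3 rule covers the additional measures only; 11.3.1 uses stratum size as its condition, and overall differences with intervals are promised.
- **Meaning.** The wording can be read as interaction or as covariate adjustment. Section 11.3.3 opens by carrying over the strategies of 11.3.2, where the factors enter as covariates. Its reference to outcomes between the groups leans towards interaction but does not settle it. If adjustment is meant, the power figures above do not apply. Reporting would still depend on the test result.
- **Inputs.** A reader might also infer that real failures in grafts would be hidden most of the time. That holds for moderate effects only. The graft share and effect size are assumptions, and a 40-point excess would be flagged more often than not. Nor can both factors be said to give small strata: lesion number should split about 60/40 by patient, although power there is also low.
- **Chance findings.** The eight tests are not independent. Restenosis or occlusion leading to reintervention or abandonment is a reportable adverse event (9.6) and also defines loss of patency (Appendix D). Clinical success needs one dialysis session, and all patients in the earlier study could resume dialysis, so that test may have almost no events. The 34% is probably high.
- **Usefulness.** Graft estimates will be imprecise.

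The last point does not rescue the rule. A wide interval shows how little is known about grafts; leaving the result out does not.

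**Conclusion.** The concern holds for the four additional measures. The plan states a rule that selects stratum results on significance, and no other section supplies them unconditionally. Under an assumed two-sided 0.05 interaction test, a 20-point graft-only excess in 90-day patency loss would go unreported about 70% to 80% of the time at graft shares of 15% to 40%, with less suppression for larger effects. Up to about 34% of trials with no true differences would report at least one chance difference, on an independence assumption that probably overstates it.

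The fault lies in exploratory reporting. It should be corrected, but it does not touch the primary test, the Holm-controlled secondary tests or the overall comparison of the arms.

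**What to change.** In 11.3.3, delete the closing condition that makes reporting depend on the test. Replace it with a commitment such as: the between-group difference and its 95% CI will be given for fistula and for graft, and for one-lesion and for two-lesion patients, whatever any test shows, and labelled exploratory. In the same place, state whether interaction or adjustment is intended and, if a test is kept, its form and level.

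Show the primary endpoint by the same strata, descriptively, in that table. The stratum-size condition in 11.3.1 may stay for formal testing, preferably with a number attached.

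The cost is one table from data and strata already collected. The downside is wide graft intervals: about ±21 to 35 points for patency and ±14 to 23 points for adjunctive therapy at graft shares of 40% down to 15%. The exploratory label should make clear that such intervals support neither a claim of benefit in grafts nor a claim of its absence.
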